##### **6.1.4. Multiple Comparisons**

The type I error rate of  $\alpha = 0.05$  will be maintained for the study by using sequential (hierarchical) testing for the primary and key secondary endpoints.

The testing will be done in the following order:

1. Primary endpoint based on PV patients in mITT population

2. Primary endpoint in mITT population (ie, PV+PF patients)
3. Key secondary endpoints based on PV patients in mITT population (in the order presented in Section 2.3.2.2)
4. Key secondary endpoints in mITT population (ie, PV+PF patients) (in the order presented in Section 2.3.2.2)

The study will be declared to be a positive study if the p-value for the primary endpoint based on PV patients in the mITT population is significant at two-sided  $\alpha = 0.05$  level. The test stops as soon as an endpoint is found not statistically significant at  $\alpha=0.05$  (2-sided). The nominal p-values for subsequent tests without adjustment will be provided in the summary tables for information purpose.

All other endpoints will be considered exploratory, and no adjustments will be made for multiple comparisons.

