### Cumulative CS dose:

- Cumulative CS dose from Baseline to Week 37

If a patient receives a rituximab therapy, the CS dose up to the date of the first dose of rituximab (including CS dose on the date of the first dose of rituximab) will be included in the analyses.

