**Table 6: Efficacy Endpoints and Analysis Methods**

	Endpoint	Analysis Method
Primary	Proportion of patients who are in CR from Week 29 to Week 37 with a CS dose of $\leq 10$ mg/day	Cochran-Mantel-Haenszel test stratified by disease history (newly diagnosed or relapsing).
Secondary Endpoints (in hierarchy)	Cumulative CS dose from Baseline to Week 37	Analysis of covariance, with CS dose duration (in days) during the blinded treatment period time to study discontinuation as the covariate, with terms for treatment group, and disease history.
	Cumulative duration of CR with CS dose $\leq 10$ mg/day from Baseline to Week 37 (days)	Zero-inflated negative binomial with terms for treatment group and disease history with an offset term based on the number of days on study during the Blinded Treatment Period
	Time (Days) to first CR with a dose of $\leq 10$ mg/day from Baseline to Week 37	Log rank test stratified by disease history
	Proportion of patients with at least one disease flare/relapse from initial control of disease activity (CDA) to Week 37	Cochran-Mantel-Haenszel test stratified by disease history
	Cumulative duration of CR with CS dose $\leq 10$ mg/day from Week 37 to Week 61 (days)	Zero-inflated negative binomial with terms for treatment group and disease history with an offset term based on the number of days on study during the Blinded and unblinded Treatment Period
	Cumulative duration of CR with CS dose = 0 mg/day from Week 37 to Week 61 (days)	Zero-inflated negative binomial with terms for treatment group and disease history with an offset term based on the number of days on study during the Blinded and unblinded Treatment Period

	Endpoint	Analysis Method
Secondary Endpoints (not in hierarchy, family-wise error rate not controlled)	The proportion of patients who are in CR from Week 29 to Week 37 with a CS dose of $\leq 5$ mg/day	Cochran-Mantel-Haenszel test stratified by disease history
	The proportion of patients who have PDAI score $< 3$ from Week 29 to Week 37 with CS $\leq 10$ mg/day	Cochran-Mantel-Haenszel test stratified by disease history
	Cumulative duration of CR with a CS dose of $\leq 10$ mg/day (days) from Baseline to Week 61	Zero-inflated negative binomial with terms for treatment group and disease history with an offset term based on the number of days on study during the Open-Label Extension Period

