To ensure the overall type I error rate of  $\alpha = 0.05$  will be maintained for the study, hierarchical testing, based on a fixed sequence procedure, will be used for the primary endpoint and continuing for the key secondary endpoints. The CMH primary analysis, as described in Section 8.1, will be the starting point for the hierarchical testing. If statistical significance is declared for the primary analysis, formal hypothesis testing will continue for the key secondary endpoints in sequence (see Section 6.1.3 for sequence of testing) until a non-significant result is reached. All other p-values from secondary and exploratory endpoints, after a non-significant p-value is reached, will be considered nominal. All statistical tests will be performed using two-tailed tests.

For Cochran-Mantel-Haensel tests, if stratum cell sizes are too small based on the Mantel-Fleiss criterion (Mantel, 1980) a Pearson Chi-square test will be used instead without stratification for disease history. If expected cell counts for the unstratified test are less than 5, a Fisher's Exact test will be used.

Analysis of covariance model residuals for the key secondary endpoint evaluated graphically for normality (e.g. quantile-quantile plot) and variance homogeneity (residual plots); additionally, a Kolmogorov-Smirnov test will be performed. A non-parametric will be considered appropriate if the two-sided p-value for the test is significant at the 0.01 level. If a parametric analysis is indicated, a rank analysis of covariance (Stokes, Davis, and Koch, 2000) will be used.

All analyses will be performed on the mITT Population as described in Section 5. Due to the small number of PF subjects expected to be enrolled in the study, the randomization strata of disease type (PV, PF) will not be included as a covariate in any of the analyses.

The analyses for efficacy endpoints involving clinical assessment CR in the blinded treatment period will be performed based on data collected on on-site visits (i.e., not including data collected from remote visits) as the primary analyses. Supportive analysis will be performed by using data collected from all visits including visits performed remotely.

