## 8.2. Key Secondary Efficacy Analyses

The key secondary endpoint of Cumulative CS dose from baseline to Week 37, adjusted for time to study discontinuation will be calculated using the summation of the CS data as described in Section 6.1.9 and will be analyzed using an ANCOVA model with terms for treatment group and disease history. The estimated mean difference in cumulative CS usage (PRN1008 minus

placebo) and the associated 95% CI will be reported. Missing data for this endpoint is described in Section 6.1.5.2. The “time to study discontinuation” covariate is up to study discontinuation, first Rituximab administration if any, or the end of the blinded treatment period whichever happens first.

If outliers or skewed data is present, sensitivity analysis will be conducted on this secondary endpoint of average weekly CS usage over 36 weeks in which the data will be rank-transformed prior to analysis.

Cumulative CS dose from Week 37 to Week 61 will be analyzed similarly.

Cumulative duration of CR with CS dose  $\leq 10$ mg/day from Baseline to Week 37, will be based on a zero-inflated negative binomial model with terms for treatment group and disease history. The p-value and estimated treatment difference (parameter difference of PRN1008 minus placebo) from the negative binomial component will be reported, along with the 95% CI for the estimated parameter. The difference estimate will also be back-transformed (e.g. exponentiated) to demonstrate the relative difference in the number of pemphigus free days between treatment groups. Cumulative duration of CR with CS dose  $\leq 10$ mg/day from Baseline to Week 37 will also be summarized based on descriptive statistics.

A Kaplan Meier analysis will be used to estimate the median and other quartiles for Time (Days) to first CR with a dose of  $\leq 10$  mg/day, along with two-sided 95% confidence intervals. The number of events and censored observations will be presented as well as graphical representations of estimated survival curves. A hazard ratio for treatment comparisons will be presented, along with its 95% confidence interval, based on a Cox regression model with terms for treatment group and disease history. The endpoint will be evaluated based on a p-value from a log-rank test stratified by disease history for treatment group comparison. In addition, a landmark analysis will be done at Week 37 in the key secondary analysis and at Week 61 for the other secondary analysis.

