Descriptive statistics including number, mean, SD, SE, median, minimum, and maximum will be provided by treatment group and by visit for domain-specific GTI scores, composite GTI total score, CWS and AIS. For CWS and AIS at Week 37, analysis of covariance model with treatment, disease history as fixed effects, and baseline GTI score, baseline CS dose as covariates, will be used to test the difference of the least-square means (LS means) between the treatment groups. Difference in LS means and the corresponding 95% CI along with the p-value will be provided.

Proportion of patients with at least one disease flare/relapse from initial control of disease activity (CDA) to Week 37 will be analyzed using the same methodology as the primary endpoint as described in Section 8.1.

Cumulative duration of CR with a CS dose  $\leq 10$  mg/day from Week 37 to Week 61, and cumulative duration of CR with a CS dose = 0 mg/day from Week 37 to Week 61 will be analyzed similarly to cumulative duration of CR with CS dose  $\leq 10$ mg/day from Baseline to Week 37.

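### Cumulative corticosteroid dose: SAP 8 attaches rank ANCOVA to the wrong branch and conflicts with SAP 8.2 on which test is confirmatory; baseline steroid dose is also left out of the model.

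*SAP*

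**What the plan says.** **Choice of test.** SAP 8 (text after Table 6) calls for graphical checks of the ANCOVA residuals and a KS test. It states "A non-parametric will be considered appropriate if the two-sided p-value for the test is significant at the 0.01 level", and then "If a parametric analysis is indicated, a rank analysis of covariance" is to be used. SAP 8.2 plans an ANCOVA reported as a mean difference with a 95% confidence interval, and adds: "If outliers or skewed data is present, sensitivity analysis will be conducted on this secondary endpoint of average weekly CS usage over 36 weeks", with the data rank-transformed. Table 6 lists ANCOVA only.

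**Place in the hierarchy.** SAP 6.1.4 fixes the order: the primary endpoint in PV, the primary endpoint in the full mITT population, the three key secondaries in PV, then the same three in mITT. "The test stops as soon as an endpoint is found not statistically significant".

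**Covariates.** Table 6 has treatment, disease history and a duration term, worded "with CS dose duration (in days) during the blinded treatment period time to study discontinuation as the covariate". SAP 8.2 says the time "covariate is up to study discontinuation, first Rituximab administration if any, or the end of the blinded treatment period whichever happens first". Baseline CS dose is not in this model. The model for the Glucocorticoid Toxicity Index (GTI) in SAP 8.3 does have it: "baseline GTI score, baseline CS dose as covariates".

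**Rituximab.** SAP 6.1.5.2 counts "the CS dose up to the date of the first dose of rituximab", that day included.

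**The concern.** Two consecutive sentences in SAP 8 contradict each other. Read literally, rank ANCOVA is used when normality is not rejected, nothing is named when it is rejected, and the ANCOVA of Table 6 has no branch at all.

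Correcting the slip does not settle the matter. SAP 8 would then be a switching rule in which a KS p-value below 0.01 makes the rank test the analysis. SAP 8.2 describes no switch. Its rank analysis is a sensitivity analysis with a trigger that has no threshold, and it is run on average weekly use instead of the cumulative dose. Nothing says which section governs the p-value that enters the fixed sequence.

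Five later tests depend on that p-value: two more key secondaries in PV and three in mITT. The same endpoint then recurs in mITT, where it gates two of those five.

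Leaving out baseline CS dose is a smaller matter. Starting dose should predict cumulative dose more directly than it predicts GTI, yet only the GTI model uses it.

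**Working it through.** The documents give no SD, effect size or power for this endpoint, so there is no planned figure to reproduce. All distributional inputs below are assumptions.

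**1. Position of the test.** The order has 2 + 3 + 3 = 8 tests. Cumulative CS dose in PV is the third, so failure there closes 8 - 3 = 5 tests.

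**2. Size.** About 120 patients with a target maximum of 22 PF (protocol synopsis) gives (120 - 22)/2 = 49 PV patients per arm. The stated PV minimum of 90 gives 45.

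**3. How often the choice of test matters.** Assumed: log-normal cumulative dose with log SD 0.3, 0.45, 0.6 or 0.8; 40% newly diagnosed, shifted by 0.5 on the log scale; effect 0.5 log SD; 49 per arm. ANCOVA is least squares on treatment and disease history. The rank test uses standardised ranks within disease history and a stratified mean-score test. ANCOVA power is 54-63%.

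- ANCOVA and rank ANCOVA reach different 0.05 decisions in 12-22% of trials.
- The corrected SAP 8 rule (ranks only if KS p < 0.01) can differ from ANCOVA alone only when KS rejects and the two tests also disagree. With a plain KS test on the standardised residuals:

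| log SD | 0.3 | 0.45 | 0.6 | 0.8 |
|---|---|---|---|---|
| Decisions differ | about 0% | 1-2% | 6% | 17% |

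A KS test corrected for estimated parameters (Lilliefors) rejects more often and gives 3.9%, 10.8%, 14.6% and 21.6%.

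A second set of simulations used 45 or 60 per arm, a dose ratio of 0.70, 15% early stopping and the duration covariate. The two tests disagreed in 1-3% of trials at log SD 0.4, 18-19% at 0.7 and 21-24% at 1.0. The plain KS test rejected in 2-5%, 36-63% and 83-97% respectively. Whether the switch comes into play therefore depends mainly on skew.

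**4. Type I error.** With no effect, each test alone rejects in about 4-5% of trials, and the corrected switching rule in 4.5-5.4% (second set). Taking whichever p-value is smaller gives 6.3-7.5% across both sets.

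**5. Baseline CS dose.** With within-stratum correlation r between baseline and cumulative dose, residual variance is multiplied by 1 - r². The equivalent sample size is 98/(1 - r²). Power at an effect of 0.5 residual SD is Φ(0.5/√(1 - r²) × √(49/2) - 1.96). This effect is scaled differently from step 3.

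| r | 1 - r² | Equivalent N | Power |
|---|---|---|---|
| 0 | 1.00 | 98 | 70% |
| 0.4 | 0.84 | 117 | 77% |
| 0.5 | 0.75 | 131 | 82% |
| 0.6 | 0.64 | 153 | 87% |

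**The case against.** The strongest reply on the test is that the sentence before the slip already shows the intent. With 'non-' restored, SAP 8 is a deterministic algorithm fixed before unblinding, and it holds its error rate. SAP 8.2 labels its rank analysis as sensitivity, so the two can coexist. This stands in part. It rules out a free choice between p-values under that reading, and it makes the gated comparison (about 0-17%) the fairer measure of the remaining ambiguity than the ungated 12-22%. It does not say whether the SAP 8 switch overrides the ANCOVA in SAP 8.2 and Table 6, and that is the question that decides the gate.

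A reader might infer that the trial's type I error is inflated. The documents do not support that. Each candidate test is valid, and 6.3-7.5% would arise only if someone chose after seeing both results. The SAP places database lock before unblinding.

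On baseline dose, disease history already carries part of the information, because the minimum starting doses differ by history, and no document supplies r. Both points are correct. This is why r is taken within stratum and the item is put as a precision gain.

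A reader might also infer that the rituximab cut biases the result or leaves the target undefined. The cut in SAP 6.1.5.2 and the covariate in SAP 8.2 end at the same event, so together they describe steroid use before rescue. Counting steroid to Week 37 is a different and equally defensible target, so a gap between the two is not bias. Parts of the CS derivation are not visible, and nothing can be concluded from that. The protocol's simpler ANOVA, the SAP 10 entry that there are no changes, and the run-together covariate name in Table 6 are housekeeping: the protocol lets the SAP modify the analysis, and SAP 2.2 logs the covariate clarification.

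**Conclusion.** The SAP 8 sentence is wrong as written. Correcting it alone does not fix which test is confirmatory for the first key secondary endpoint. The consequence is an undetermined gate decision for five later tests. Under the likely reading the two candidate analyses differ in about 0-17% of trials at moderate power, negligible with mild skew and material with strong skew. These sizes rest on assumed log-normal doses, 49 PV patients per arm and a plain KS test. The textual contradiction does not depend on them.

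Omitting baseline CS dose costs precision only. The gain from adding it depends on a correlation that the documents do not give.

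The change should be made before unblinding. It does not put the trial's validity in doubt.

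**What to change.** 1. Correct the branch sentence in SAP 8. Name one confirmatory test for cumulative CS dose, the same for PV and mITT, and say so in SAP 8, 8.2 and Table 6. Make the other test a sensitivity analysis on the same variable. Remove the separate trigger in SAP 8.2 or align it with SAP 8.
2. Add baseline daily CS dose to the model, beside treatment, disease history and the existing duration covariate (SAP 8.2 and Table 6).
3. Optional, and not a correction of an error: label the current target as steroid before rescue. Add a sensitivity analysis that counts recorded CS to Week 37 without the time covariate, reported with rescue rates by arm, because it would include any steroid saving due to rituximab itself.

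The cost is SAP wording and modest programming. No new data are needed, and baseline dose uses one degree of freedom.

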## 8.1. Primary Efficacy Analysis

The primary efficacy endpoint is the proportion of patients who are in CR from Week 29 to Week 37 with a prednisone dose of  $\leq 10$  mg/day in patients treated with PRN1008 compared with placebo.

Allow  $p_0$  to represent the proportion of responders in the placebo group;  $p_1$  will represent the proportion of responders in the PRN1008 group. The null and alternative hypotheses are:

$$H_0: p_1 - p_0 = 0$$

The proportion of patients who are in CR from Week 29 to Week 37 with a prednisone dose of  $\leq 10$  mg/day does not differ between the two treatment groups.

$$H_1: p_1 - p_0 \neq 0$$

The proportion of patients who are in CR from Week 29 to Week 37 with a prednisone dose of  $\leq 10$  mg/day differs between the two treatment groups.

The primary endpoint will be analyzed using a CMH test, stratified by disease history. The observed number and proportion of subjects meeting the primary endpoint as well as the proportion difference (PRN1008 – placebo), estimated standard error (SE), 95% CI and the associated p-value will be reported.

Descriptive summaries of patients who are in CR with a CS dose of  $\leq 10$  mg/day will also be provided by visit through Week 37.

*These analyses will be performed on the mITT Population as well as in study subgroups as described in Section 6.1.3.2.* As a sensitivity analysis to the primary endpoint, disease type will be included as an additional stratification factor in the CMH test.

Tipping point analyses (Yan, 2009) will be done to investigate the impact of missing data and lost to follow-up (LTF). The tipping point analysis will look at all possible combination of converting missing data to a responder, starting at 0 and ending at all are responders. The cases where the statistical significance tips from significance to non-significance (defined as a two sided p-value  $> 0.05$ ) will be listed. A complete list of all combinations will also be presented. If the imbalances that leads to a change in interpretation are clinically implausible then the results of the primary analysis will be deemed reliable.

In addition, the following endpoints will be analyzed as supportive analyses to primary endpoint:

- Time to first CDA from Baseline to Week 37
- Time to CR from Baseline to Week 37

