## Study Population

Approximately 120 male or female patients with newly diagnosed or relapsing moderate to severe pemphigus (pemphigus vulgaris [PV] or pemphigus foliaceus [PF]) will be enrolled with a targeted minimum of 90 patients with PV, and a target maximum of 22 patients with PF.

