### 3.4. Treatments Administered

Patients will be randomized to one of two treatments in a 1:1 allocation ratio:

- 400 mg of PRN1008
- matching placebo

Study investigational product (IP) taken twice daily by mouth starting on Day 1.

Required, initial doses of CS for the duration of Screening are  $\geq 0.2$  mg/kg/day of CS for patients with relapsing disease (diagnosed  $> 6$  months prior to Screening) and  $\geq 0.5$  mg/kg/day for patients with newly diagnosed disease (diagnosed  $\leq 6$  months prior to Screening). At Screening, patients will begin to take Sponsor-provided CS according to the minimum dose requirements, and as required to adequately treat the disease during the Screening period. CS doses may be adjusted per Investigator discretion during the Screening period, but the dose should not be reduced below the required minimum initial dose levels.

Thereafter, CS will be managed per the Corticosteroid and Rituximab Management protocol detailed in Appendix 1 of the protocol.

Rituximab treatment may also be administered during the Blinded Treatment Period after the Week 5 visit, unless contraindicated, after a second or subsequent, clinically significant “qualifying relapse” occurs. Full details on Rituximab treatment can be found in Appendix 1 of the protocol.

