## 4. Statistical Analysis and Reporting

### 4.1. Introduction

Data processing, tabulation of descriptive statistics, calculation of inferential statistics, and graphical representations will be performed primarily using SAS (release 9.4 or higher). If the use of other software is warranted, the final statistical methodology report will detail what software was used for what purposes.

Continuous (quantitative) variable summaries will include the number of subjects ( $n$ ) with non-missing values, mean, standard deviation (SD), median, minimum, and maximum.

Categorical (qualitative) variable summaries will include the frequency and percentage of subjects who are in the particular category or each possible value.

Analyses will be presented by the treatment group assigned at randomization for the Blinded Treatment Period of the study and by double-blind treatment group and overall for the Open Label Phase and Long-Term Extension Phase of the study, unless stated otherwise.

The minimum and maximum will be reported with the same degree of precision (i.e., the same number of decimal places) as the observed data. Measures of location (mean and median) will be reported to 1 degree of precision more than the observed data and measures of spread (SD) will be reported to 2 degrees of precision more than the observed data.

Percentages will be presented to 1 decimal place, unless otherwise specified.

Unless otherwise indicated, all statistical tests will be conducted at the 0.05 significance level using 2-tailed tests, and  $P$  values will be reported. Corresponding 95% confidence intervals (CIs) will be presented for statistical tests.

Statistical testing will be performed at the 0.05 level using two-tailed tests.

To control for the overall type I error rate, hierarchical testing based on a fixed sequence procedure will be used. If statistical significance is declared for the primary analysis, formal hypothesis testing will be done for the key secondary endpoints in sequence until a non-significant result is reached. All other  $p$  values from key secondary and other secondary endpoints, after a non-significant  $p$  value is reached, will be considered nominal.

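### Baseline PDAI and baseline CS dose, both already collected, are left out of the analyses of the primary endpoint and key secondaries 2 and 3: a modest loss of efficiency, not of validity

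*SAP*

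**What the plan says.** SAP 6.1.3.1 makes disease history the covariate or stratification factor throughout and excludes disease type. The three CR endpoints in the testing hierarchy follow that rule:

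- **Primary (SAP 8.1):** "The primary endpoint will be analyzed using a CMH test, stratified by disease history". A sensitivity analysis adds disease type as a second stratification factor. Under SAP 8, if the strata are too sparse, the test becomes an unstratified chi-square or Fisher's exact test, so disease history drops out as well.
- **Key secondary 2, cumulative duration of CR (SAP 8.2):** the analysis "will be based on a zero-inflated negative binomial model with terms for treatment group and disease history". SAP Table 6 adds an offset for days on study.
- **Key secondary 3, time to first CR (SAP 8.2):** the p-value comes from a log-rank test stratified by disease history. The hazard ratio is "based on a Cox regression model with terms for treatment group and disease history".

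Other models use more. The GTI analysis takes "baseline GTI score, baseline CS dose as covariates" (SAP 8.3), and the PDAI repeated-measures model includes baseline PDAI. Protocol Table 2 schedules PDAI before dosing on Day 1. SAP 6.1.3.2 makes PDAI severity (9-45 vs 46 or more) a subgroup for the primary and key secondary endpoints.

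**The concern.** A responder must be free of lesions at Weeks 29, 33 and 37 on no more than 10 mg/day of CS (Protocol 8.5.1). The amount of disease to clear and the dose to taper from are natural candidate predictors of that outcome. Disease history captures them only in part: it sets the entry PDAI thresholds and the minimum starting CS doses (Protocol Table 1), but actual doses follow investigator judgment.

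The first test in the hierarchy rests on roughly 45 to 49 PV patients per arm, and every later test depends on it. With arms of that size, a chance imbalance in PDAI or CS dose is possible, and no planned analysis of the overall comparison allows for it. A subgroup table shows results by severity but does not adjust the overall contrast. If the two variables are prognostic, some precision also goes unused.

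**Working it through.** **Inputs from the documents**
- Test level: "all statistical tests will be conducted at the 0.05 significance level using 2-tailed tests" (SAP 4.1).
- Allocation: "Patients will be randomized to one of two treatments in a 1:1 allocation ratio" (SAP 3.4).
- Size: "Approximately 120 male or female patients with newly diagnosed or relapsing moderate to severe pemphigus", with a "targeted minimum of 90 patients with PV, and a target maximum of 22 patients with PF" (Protocol, Study Population). PV per arm is therefore 90/2 = 45 at the targeted minimum, or (120 − 22)/2 = 49 if the PF cap is filled.
- Response rates: the current sample-size sections show only the endpoint. The amendment history (Protocol 12.13.9) gives 50% vs 15%, with at least 55 per group and power above 90%. It was written for the former 5 mg/day endpoint.

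**Assumptions (not in the documents):** prognostic strength of the baseline variables, and any other response rates.

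**1. The plan's own figure.** Power = Φ{[d − 1.96√(2p̄(1−p̄)/n)] / √([p₁(1−p₁)+p₀(1−p₀)]/n)}. With p₁ = 0.50, p₀ = 0.15, d = 0.35, p̄ = 0.325:
- n = 45: (0.35 − 1.96 × 0.0987)/0.0916 = 1.71, power 95.6%.
- n = 49: (0.35 − 1.96 × 0.0946)/0.0878 = 1.87, power 97.0%.
- n = 55: power 98.3%.

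The stated power above 90% is reproduced.

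**2. Why CS dose is a candidate.** From Protocol Table 6, 60 to 20 mg is 4 steps × 2 weeks = 8 weeks, and 20 to 10 mg is 4 weekly steps = 4 weeks. From ECP, 10 mg is thus about 12 weeks away from 60 mg and 4 weeks away from 20 mg. To be at 10 mg by Week 29, ECP is needed by about Week 29 − 12 = 17 or Week 29 − 4 = 25 respectively. The documents allow no comparable calculation for PDAI.

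**3. Size of the CMH test.** In simulation at 15% vs 15% (45 or 55 per arm, 4,000 runs, odds ratio 1 to 3 per SD of a baseline score), CMH rejected in 4.6% to 5.6% of runs. The Monte Carlo SE is √(0.05 × 0.95/4000) = 0.3 points. Leaving the covariates out does not inflate type I error.

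**4. Power, CMH vs a logistic score test adjusted for disease history and a baseline score, uncalibrated**

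| Response | Per arm | Log-odds per SD | CMH | Adjusted |
|---|---|---|---|---|
| 50% vs 15% | 49 | 0.5 / 0.8 / 1.1 | 97.1 / 96.8 / 97.0% | 97.6 / 98.2 / 98.8% |
| 38% vs 15% | 49 | 0.5 / 0.8 / 1.1 | 74 / 72 / 74% | 76 / 78 / 82% |
| 35% vs 15% | 45 | 0.69 / 1.10 | 59.9 / 60.0% | 64.4 / 68.2% |

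These favour adjustment slightly. At 49 per arm the score test had a size of up to 6.2%, against 4.3% to 5.2% for CMH. With both covariates fitted and both tests calibrated to 5%, the gain at 49 per arm is about 0 to 7 points at 15% vs 38% and at most about 2 at 15% vs 50%. About 1 point is lost if neither covariate is prognostic.

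**5. Analytic cross-check.** If the covariates explain a share R² of outcome variance beyond disease history, effective n = n/(1 − R²). With R² = 0.10 and n = 45, effective n is 50: power moves from 95.6% to 97.2% at 50% vs 15%, and from 59.4% to 64.0% at 35% vs 15%.

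**6. Time to first CR.** Assuming 50% vs 25% with an event by Week 37 and 45 per arm, the stratified log-rank test vs a covariate-adjusted Cox score test has power 71.0% vs 73.8%, 70.4% vs 78.9% and 71.8% vs 88.3% at hazard ratios of 1.5, 2 and 3 per SD. Cumulative duration of CR was not simulated, because the documents give no inputs for it.

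**The case against.** The case for leaving the plan alone is substantial.

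- Randomisation protects the test. A reader might infer that the unadjusted comparison is biased or invalid; step 3 shows otherwise.
- A reader might infer that baseline PDAI and Day 1 CS dose are known to drive CR. No passage estimates either relation. The taper starts at ECP, not Day 1, and the dose may be raised by 50% to 100% at a time before ECP (Protocol Appendix 1), so Day 1 dose is not the taper-start dose. The taper arithmetic also bears more on time to first CR than on a status read at Weeks 29 to 37.
- PDAI is not ignored: severity is a prespecified subgroup, and disease history is a partial proxy for both variables.
- The summary of changes for Amendment 07 records removal of a reference to severity-adjusted sensitivity analyses of the primary, so their absence looks deliberate.
- CMH matches the hypothesis on the difference in proportions, needs no linearity in CS dose and has a sparse-data fallback. At 15% vs 38% about 49 × 0.15 + 49 × 0.38 = 26 responders would support four coefficients.

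All of this stands, and it rules out replacing the confirmatory test. It does not answer the narrower point that no planned analysis of these three endpoints adjusts for either variable.

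**Conclusion.** The point holds as one of efficiency and robustness. The three CR endpoints adjust for disease history only, while two plausible baseline predictors are at hand and used in other models. The power at stake for the primary is small if the true effect is near 50% vs 15% and moderate if it is smaller. Those figures rest on assumed prognostic strengths, and the 15% vs 38% and 15% vs 35% scenarios are also assumptions.

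One further inference should be resisted: that adding terms to the Cox model strengthens the formal test of key secondary 3. That endpoint is judged by the stratified log-rank p-value, so the gains in step 6 would arise only if the test itself were changed.

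**What to change.** Keep the stratified CMH as the confirmatory test. Before unblinding:

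1. **Primary:** prespecify as the first supportive analysis a logistic model with treatment, disease history, log(baseline PDAI total activity + 1) and baseline CS dose. Report the standardised risk difference with its CI, in PV patients and in the full mITT population.
2. **Key secondary 2:** add the same two baseline terms to the zero-inflated negative binomial model, stating which component or components carry them. This model supplies the p-value in the hierarchy, so the choice must be settled before unblinding.
3. **Key secondary 3:** add the same terms to the Cox model that supplies the hazard ratio. Label that ratio as conditional on them, and note that the log-rank p-value is unchanged.
4. **Fallback:** state that a model that fails to converge reverts to disease history only.

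The cost is SAP wording and model terms, with no new data. The downside is extra parameters with few responders: 26/4 = 6.5 per coefficient in the logistic model at 15% vs 38%.
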